9.3 Primary Efficacy Endpoint and Analyses

9.3.1 Primary Efficacy Endpoint

The primary endpoint is the achievement of HiSCR at Week 12. HiSCR is defined as at least a 50% reduction in the total AN count with no increase in abscess count and no increase in draining fistula count relative to Baseline.

The corresponding statistical null hypothesis to the primary endpoint is that there is no difference between upadacitinib 30 mg and historical placebo rate, in the proportion of subjects achieving HiSCR at Week 12.

9.3.2 Main Analysis of Primary Efficacy Endpoint

Analysis of the primary endpoint will be conducted in the ITT Population based on treatment as randomized. Comparison of the primary endpoint will be made between upadacitinib 30 mg group and historical placebo rate (25%) using a one sample Chi-square test at Week 12. Point estimates, p-value and 95% CIs for the difference in proportions between upadacitinib 30 mg and the historical placebo rate (25%) will be provided.

The attributes of the estimands corresponding to the primary efficacy endpoint are summarized in [Table 1](#).

Table 1. Summary of the Estimand Attributes of the Primary Efficacy Endpoint

Attributes of the Estimand					
Estimand	Treatment	Endpoint	Population	Intercurrent Events	Statistical Summary
Primary efficacy endpoint of HiSCR	Upadacitinib 30 mg QD	Achievement of HiSCR at Week 12 without the initiation of antibiotics for HS-related infections or discontinuation of study drug due to lack of efficacy	All randomized subjects (ITT Population)	The intercurrent of initiation of antibiotics for HS-related infections or discontinuation of study drug due to lack of efficacy are included in the endpoint attribute using composite variable strategy. No other intercurrent event is considered.	Difference between upadacitinib 30 mg and placebo in the proportion of subjects achieving HiSCR at Week 12

9.3.3 Sensitivity Analyses of the Primary Efficacy Endpoint

Historical placebo data pre-selected by propensity score matching combined with in-trial placebo data will be used to estimate treatment effect of upadacitinib against placebo. Subjects with historical placebo data of HiSCR were pre-selected using propensity score matching from two Humira Phase 3 studies (M11-313 and M11-810) and the Risankizumab study (M16-833), whose study populations, entry criteria and study designs are similar to this study.

The propensity scores were estimated for all randomized subjects in this study and historical placebo subjects with selected common baseline demographics and characteristics variables:

- Age
- Gender
- Race
- Smoking status
- Baseline BMI

- Baseline AN count (abscess count and inflammatory nodule count)
- Duration of HS since diagnosis
- Baseline Hurley Stage
- Baseline draining fistula

The "nearest neighbor matching" were performed based on a distance measure, caliper, with the propensity score for each subject calculated from the logistic regression. The number of synthetic placebo subjects was determined by the simulation results, for each in-trial placebo rate assumption, with pre-determined criteria that the number of synthetic placebo subjects not to exceed 68 (approximately 3 times the number of in-trial placebo subjects) and the one-sided false positive rate was controlled at 10% (simulation details can be found in [Appendix F](#) and the list of matching subjects can be found in [Appendix G](#):

In-Trial Placebo Rate	Number of Synthetic Placebo Subjects
≤ 33%	68
>33% and ≤ 34%	23*
>34%	0

* The 23 subjects with the highest rank in [Appendix G](#) Table A will be used in the analysis.

After database lock, comparison between the in-trial data of the upadacitinib group and the in-trial placebo data combined with the pre-selected historical placebo subjects' data will be performed. Frequencies and percentages will be summarized along with 95% confidence interval (CI). Pairwise comparisons of upadacitinib vs. placebo will be made using CMH test. Point estimates, *p*-value and 95% CIs for the difference in proportions between each upadacitinib group and placebo will be provided. The stratification factors (prior exposure to anti-TNF [yes, no], Hurley Stage [$<$ III, III]) will be adjusted in the model.

Comparison between the in-trial data of the upadacitinib group and the in-trial placebo subjects will also be performed. The analysis method will be the same as described above.

The NRI-C will be the primary approach for missing data handling in the analysis of the primary efficacy endpoint. NRI-NC and MI will be used as sensitivity analysis.

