2.3 Treatment Assignment and Blinding

Subjects will be randomized to upadacitinib 30 mg QD or placebo in a 2:1 ratio. Randomization will be stratified by anti-TNF use prior to baseline (yes or no) and Hurley stage (< III or III).

All AbbVie personnel with direct oversight of the conduct and management of the trial (with the exception of AbbVie Drug Supply Management Team), the investigator, study site personnel, and the subject will remain blinded to each subject's treatment through Week 12. Sites and subjects will remain blinded for the duration of the study.

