9.4 Secondary Efficacy Analyses

9.4.1 Main Analyses of Secondary Efficacy Endpoints

The secondary endpoint NRS30, defined as the achievement of at least 30% reduction and at least 1 unit reduction from Baseline in Patient's Global Assessment (PGA) of Skin Pain (numeric rating scale [NRS]) – at worst at Week 12 among subjects with baseline NRS ≥ 3 .

NRS30 will be analyzed using the same method as for the primary endpoint and comparing with the historical placebo rate (22.5%) at Week 12. The historical placebo rate of 22.5% is assumed based on the response rate of placebo subjects from the two Humira studies (Study M11-313 and Study M11-810), who satisfied the same eligibility criteria.

The same supplemental analysis to compare upadacitinib 30 mg group vs in-trial placebo group combined with pre-selected placebo subjects' data from the three existing trials will also be performed as described in Section 9.3.3. The actual number of synthetic placebo subjects is determined as below (simulation details can be found in [Appendix F](#) and the list of matching subjects can be found in [Appendix G](#)):

In-Trial Placebo Rate	Number of Synthetic Placebo Subjects
$\leq 36\%$	68
$>36\%$ and $\leq 37\%$	23*
>37	0

* The 23 subjects with the highest rank in [Appendix G](#) Table B will be used in the analysis.

Comparison between the in-trial data of the upadacitinib group and the in-trial placebo subjects will also be performed. The analysis method will be the same as described in Section 9.3.3.

In addition, analgesic use will be handled as follows:

- Prohibited analgesic (including opioids): A subject will be counted as a non-responder from the day that the subject initiates prohibited analgesic to 5 days after the end of such analgesic use.
- Protocol-allowed analgesic use:
 - A subject who enter the study without concomitant analgesic will be counted as a non-responder from the day that the subject initiates a protocol-allowed analgesic to 2 days after the end of such analgesic use.
 - A subject who entered the study on a stable dose of a protocol-allowed concomitant analgesic will be counted as a non-responder from the first day of an analgesic dose increase to 2 days after the end of the dose increase.

The NRI-C will be the primary approach for missing data handling in the analysis of the secondary efficacy endpoint. NRI-NC will be used as sensitivity analysis.

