1.0 Introduction

In randomized controlled trials, randomization ensures that the different arms of the trial tend to be balanced, both in terms of measured and unmeasured characteristics of the population. Thus, the only systematic difference between treated and untreated patients is the exposure to treatment. This allows one to obtain unbiased estimates of the average treatment effect within the context of the study design. In the studies such that the treatment effect will be estimated with the combination of in-trial placebo subjects and historical placebo subjects, the distribution of subject characteristics is likely to vary systematically between the in-trial subjects and historical subjects and is often related to patient prognosis, patient characteristics, and physician preference. Thus, confounding may occur.

Propensity score matching method (Rosenbaum and Rubin, 1985) matches in-trial patients with synthetic placebo subjects based on propensity scores such that matched in-trial subjects and placebo subjects are comparable in terms of covariates used in propensity score determination. This process mimics randomization to create two comparable groups with a caution of limitation that the matching is conditional on included covariates.

To provide the guidance on how many synthetic placebo subjects can be matched for the primary and secondary analysis (HiSCR and NRS30), simulations have been conducted to evaluate the power and false positive rate of combining the data from historical placebo subjects and in-trial subjects under different scenarios.

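### The NRS30 comparison with borrowed historical placebo neither matches on nor adjusts for baseline skin pain, a value every borrowed subject must already have

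*SAP*

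**What the plan says.** SAP 9.3.3 estimates propensity scores from "selected common baseline demographics and characteristics variables": age, gender, race, smoking status, BMI, AN count, HS duration, Hurley stage and draining fistula. The combined comparison is a CMH test adjusted for two factors: "The stratification factors (prior exposure to anti-TNF [yes, no], Hurley Stage".

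SAP 9.4.1 defines NRS30 as a reduction of at least 30% and at least 1 unit from Baseline, "at worst at Week 12 among subjects with baseline NRS" of 3 or more. It states that the supplemental comparison with borrowed placebo "will also be performed as described in Section 9.3.3". NRS30 has its own ranked list (Appendix G Table B) and its own borrowing cut-offs: 68 subjects if the in-trial placebo rate is at most 36%, 23 if above 36% and at most 37%, none above that. No separate covariate set is given for NRS30.

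Appendix F, section 1.0, describes the matching "with a caution of limitation that the matching is conditional on included covariates". Appendix F, section 2.1, lists the simulated baseline covariates; baseline pain is not among them.

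**The concern.** A propensity match balances only what is in the model. For HiSCR the model contains the baselines of the endpoint's components, AN count and draining fistula. The MMRM and ANCOVA models in SAP 9.2.2 likewise include each continuous endpoint's own Baseline. NRS30 is the exception.

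Baseline pain fixes the size of fall needed. By the definition, a subject starting at 3 needs a 1-point fall (30% is 0.9, so the 1-unit minimum applies), and a subject starting at 10 needs a 3-point fall. Baseline pain may also be prognostic, although the documents do not say how strongly.

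Missing data cannot explain the omission. NRS30 cannot be derived for a historical subject without a baseline pain value, so each borrowed subject must have one. If the borrowed subjects differ from the trial in baseline pain, the pooled placebo rate moves and the comparison absorbs the difference as apparent drug effect, or hides real effect.

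**Working it through.** **The plan's own figures.** The SAP gives no figure for this omission. The nearest are the Appendix F false-positive rates, which describe a general gap between in-trial and historical placebo rates. For NRS30 with 68 matched they are 0.012 at no gap, 0.038 at +5 points and 0.096 at +10 points. A simplified unstratified calculation (45 vs 23 + 68, historical rate 26%) does not reproduce them: it gives 0.024 to 0.046 at no gap and 0.188 to 0.219 at +10 points. It lacks the matching and stratification of the SAP's simulation, so the mismatch is not evidence of an error. The rates below should be compared with nominal 0.05, not with that table.

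**Inputs from the documents.** 45 upadacitinib and 23 placebo subjects (Appendix F, section 2.1); at most 68 borrowed (SAP 9.3.3 and 9.4.1); NRS30 historical placebo rate 26% (Appendix F, section 3.2); one-sided alpha 0.05 (SAP 9.1). The arm sizes are upper bounds, because subjects with baseline NRS below 3 do not count. Hence 23 + 68 = 91 is the most placebo subjects possible, and 68/91 = 75% is the least the historical share can be when all 68 are used.

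**Assumptions, not in the documents.** Share with high pain in trial f_T = 0.5; share in the borrowed set f_H = 0.3 to 0.8; response lower by d = 0.10 to 0.20 with high pain; no drug effect; all 68 borrowed.

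**Step 1, shift in the apparent treatment difference.** Shift = (68/91) × (f_H − f_T) × d.
- f_H = 0.8, d = 0.20: 0.747 × 0.3 × 0.20 = +0.045
- f_H = 0.3, d = 0.20: 0.747 × (−0.2) × 0.20 = −0.030

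**Step 2, approximate false-positive rate.** At 26%, p(1−p) = 0.1924. SE = √[0.1924 × (1/45 + 1/91)] = 0.080. Rate = 1 − Φ(1.645 − shift/SE).
- +0.045: 1 − Φ(1.645 − 0.561) = 0.139
- −0.030: 1 − Φ(1.645 + 0.374) = 0.022

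**Step 3, simulation under the null (20,000 runs per row).**

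| f_H | d | Not matched or adjusted |
|---|---|---|
| 0.3 | 0.10 | 0.033 |
| 0.3 | 0.20 | 0.023 |
| 0.5 | 0.10 | 0.050 |
| 0.5 | 0.20 | 0.049 |
| 0.7 | 0.10 | 0.075 |
| 0.7 | 0.20 | 0.107 |
| 0.8 | 0.10 | 0.091 |
| 0.8 | 0.20 | 0.146 |

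With adjustment for pain, the rate lies between 0.0505 and 0.0544 in every row. The hand calculation and the simulation agree on size and direction.

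**Step 4, would the borrowing cut-offs catch it?** The largest assumed gap between in-trial and historical placebo rates is 0.3 × 0.20 = 6 points. The standard error of a 26% rate in 23 subjects is √(0.1924/23) = 0.091, about 9 points. A gap of this size is below one standard error, so the cut-offs cannot detect it reliably.

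**The case against.** **The analysis is supplemental and has a backstop.** This stands. The main NRS30 test uses a fixed 22.5% rate and the primary HiSCR test a fixed 25%; neither uses the match. An in-trial-only comparison is prespecified for both endpoints, and Appendix F openly limits comparability to the included covariates.

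**The NRS30 covariates are inferred.** This partly stands. The list in 9.3.3 is introduced for HiSCR, and the contents of Appendix G are not in the text available for review. But 9.4.1 points to 9.3.3 for the method and names no other covariates.

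**The definition already handles baseline.** Only in part. A relative reduction with a floor of 3 narrows the range of baseline pain but does not balance it between 3 and 10.

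**Re-matching now means re-selecting comparators whose outcomes are known.** This is a fair caution. It is met by fixing the model on covariates alone, or by adjusting in the analysis and leaving the list as it is.

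**Stronger readings that a reader might infer.** One is that leaving prior anti-TNF out of the match biases both endpoints. The documents do not support that, because the planned CMH test stratifies on it. With 15% exposed in trial (5% + 10% in Appendix F), assumed historical shares of 0% to 45% and response 10 to 20 points lower if exposed, the stratified false-positive rate is 0.049 to 0.054. If no historical subject is exposed, that stratum simply compares in-trial drug with in-trial placebo. Another is that the rise to 0.096 in the NRS30 table measures this omission. It does not: it describes a general 10-point gap, larger than any produced by the assumptions above.

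**Conclusion.** The point holds for the supplemental NRS30 comparison with borrowed placebo, and only there. As written, the plan neither matches on nor adjusts for baseline pain beyond the baseline NRS restriction, while historical subjects may form three quarters or more of the comparator. Under the stated assumptions the false-positive rate lies between about 0.02 and 0.15 instead of about 0.05. The direction is unknown: more high-pain subjects in the borrowed set would favour the drug, and fewer would count against it. The range depends on assumed pain shares and an assumed prognostic effect. If pain happens to be balanced, there is no distortion. This is a cheap improvement to a secondary line of evidence, not a flaw in the main test of either endpoint.

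**What to change.** Before database lock, and while in-trial treatment remains blinded, do one of the following:

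- **Re-match.** Add baseline pain NRS to the NRS30 propensity model among subjects with baseline NRS of at least 3. Write the model down before running it, regenerate Appendix G Table B, and re-check the 36% and 37% cut-offs in Appendix F.
- **Adjust.** Keep the existing list and adjust the combined NRS30 analysis for baseline pain. This avoids re-selecting comparators.

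In either case, state the NRS30 covariate set in 9.4.1, and report standardised differences between in-trial and borrowed subjects for baseline pain and prior anti-TNF exposure. Prior anti-TNF need not enter the match.

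Cost: re-matching needs a re-run of the match and of the NRS30 simulation, and may loosen the match slightly on other covariates. Adjustment needs a short SAP change. Neither needs new data.

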9.4 Secondary Efficacy Analyses

9.4.1 Main Analyses of Secondary Efficacy Endpoints

The secondary endpoint NRS30, defined as the achievement of at least 30% reduction and at least 1 unit reduction from Baseline in Patient's Global Assessment (PGA) of Skin Pain (numeric rating scale [NRS]) – at worst at Week 12 among subjects with baseline NRS ≥ 3 .

NRS30 will be analyzed using the same method as for the primary endpoint and comparing with the historical placebo rate (22.5%) at Week 12. The historical placebo rate of 22.5% is assumed based on the response rate of placebo subjects from the two Humira studies (Study M11-313 and Study M11-810), who satisfied the same eligibility criteria.

The same supplemental analysis to compare upadacitinib 30 mg group vs in-trial placebo group combined with pre-selected placebo subjects' data from the three existing trials will also be performed as described in Section 9.3.3. The actual number of synthetic placebo subjects is determined as below (simulation details can be found in [Appendix F](#) and the list of matching subjects can be found in [Appendix G](#)):

In-Trial Placebo Rate	Number of Synthetic Placebo Subjects
$\leq 36\%$	68
$>36\%$ and $\leq 37\%$	23*
>37	0

* The 23 subjects with the highest rank in [Appendix G](#) Table B will be used in the analysis.

Comparison between the in-trial data of the upadacitinib group and the in-trial placebo subjects will also be performed. The analysis method will be the same as described in Section 9.3.3.

In addition, analgesic use will be handled as follows:

- Prohibited analgesic (including opioids): A subject will be counted as a non-responder from the day that the subject initiates prohibited analgesic to 5 days after the end of such analgesic use.
- Protocol-allowed analgesic use:
 - A subject who enter the study without concomitant analgesic will be counted as a non-responder from the day that the subject initiates a protocol-allowed analgesic to 2 days after the end of such analgesic use.
 - A subject who entered the study on a stable dose of a protocol-allowed concomitant analgesic will be counted as a non-responder from the first day of an analgesic dose increase to 2 days after the end of the dose increase.

The NRI-C will be the primary approach for missing data handling in the analysis of the secondary efficacy endpoint. NRI-NC will be used as sensitivity analysis.

9.5 Additional Efficacy Analyses

9.5.1 Additional Categorical Endpoints in Period 1

The analysis of flare during Period 1 will be performed using the same method as for the primary endpoint, comparing with historical placebo rate of the occurrence of flare in 12 weeks (34%). The historical placebo rate is assumed based on the response rate of placebo subjects from the two Humira studies (Study M11-313 and Study M11-810), who satisfied the same eligibility criteria. A supplemental analysis will be performed to compare upadacitinib 30 mg and in-trial placebo group.

9.5.2 Additional Continuous Endpoints in Period 1

Continuous endpoints except for DLQI will be analyzed using MMRM including observed measurements at all visits, as described in Section 9.2. For HSSA total score, HS-related swelling, odor, worst drainage, and HSIA at Week 12, the comparison will be made between upadacitinib 30 mg group and the historical change from baseline at Week

12 values of -0.72, -0.8, -0.72, -0.89 or -0.83 (HSIA historical value is the average of Week 8 and Week 16 since there is no Week 12 measurement), respectively, using MMRM. The historical change from baseline at Week 12 values are obtained based on the placebo subjects from Risankizumab Study M16-833, who satisfied the same eligibility criteria.

For change from baseline in DLQI at Week 12, the comparison will be made between upadacitinib 30 mg group and historical change from baseline (-2.5) using an ANCOVA model. The historical change from baseline of -2.5 is assumed based on the mean change from Baseline of placebo subjects from the two Humira studies (Study M11-313 and Study M11-810), who satisfied the same eligibility criteria.

Continuous endpoints will also be analyzed using MMRM for endpoints other than DLQI and ANCOVA for DLQI to compare upadacitinib 30 mg QD with in-trial placebo group.

9.5.3 Summary of Long-Term Efficacy

Long-term efficacy in Period 2 will be summarized by visit for ITT Population using the observed case approach, as described in Section [9.2.3](#).

9.6 Efficacy Subgroup Analyses

To evaluate the consistency of the efficacy over demographic and other baseline characteristics, summaries will be provided for the following subgroups for the primary efficacy endpoint.

- Age group (< 40 years, ≥ 40 – < 65 years, ≥ 65 years)
- Sex (male, female)
- Race (white, non-white)
- Smoking (current, ex or never)
- Body mass index (normal: < 25, overweight: ≥ 25 – < 30, obese: ≥ 30)
- Duration of HS since diagnosis (by median)
- Prior exposure to TNF antagonists (yes, no)

- Baseline Hurley stage (< III, III)

For age and BMI subgroups with fewer than 10% subjects will be combined with their adjacent subgroup.

10.0 Safety Analyses

10.1 General Considerations

Safety data will be summarized for each safety population. Safety summaries will be presented by treatment group. For ALL_UPA Population, upadacitinib 30 mg, 15 mg and a total group for all subjects on upadacitinib will be summarized. For the safety analysis, subjects are assigned to a treatment group based on the treatment actually received, regardless of the treatment randomized.

A subject's actual treatment sequence will be determined by the most frequent dose regimen received in Period 1.

10.2 Adverse Events

Adverse events (AEs) will be summarized and presented using primary MedDRA System Organ Classes (SOCs) and preferred terms (PTs) according to the version of the MedDRA coding dictionary used for the study at the time of database lock. The actual version of the MedDRA coding dictionary used will be noted in the AE tables and in the clinical study report. Specific adverse events will be counted once for each subject for calculating percentages, unless stated otherwise. In addition, if the same adverse event occurs multiple times within a subject, the highest severity and level of relationship to investigational product will be reported.

10.2.1 Treatment-Emergent Adverse Events

For Period 1, treatment-emergent adverse events (TEAEs) are defined as any adverse events that begin or worsen in severity after initiation of study drug through 30 days following the last dose of study drug in Period 1 or first dose in Period 2, whichever is

earlier. For Period 2, TEAEs are defined as any adverse events that begin or worsen in severity after initiation of study drug through 30 days following the last dose of study drug in Period 2. Events where the onset date is the same as the study drug start date are assumed to be treatment-emergent. All TEAEs will be summarized overall, as well as by primary MedDRA SOC and PT. The SOCs will be presented in alphabetical order, and the PTs will be presented in alphabetical order within each SOC.

The number and percentage of subjects experiencing TEAEs will be summarized.

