6 STUDY DRUG

6.1 Treatments Administered

Study drug will be taken orally once daily, beginning on Day 1 (Baseline), and should be taken at approximately the same time each day, with or without food.

Study drug includes the investigational product of upadacitinib and matching upadacitinib placebo. Details regarding study drug dosing and administration are provided in the Study Drug section of the Protocol. The study drug will be dispensed at the visits listed in Section 2.1.

Study drug must not be dispensed without contacting the IRT system. Study drug may only be dispensed to subjects enrolled in the study through the IRT system. At the end of the Treatment Period or at the Premature D/C visit, the site will contact the IRT system to provide visit date information and study drug return information for each kit.

AbbVie will not supply any disease-related concomitant medication (indication) therapy taken during the course of the study.

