6.0 Study Drug Duration and Compliance

For each safety population, duration of treatment will be summarized for each treatment group and for all dose groups combined. Duration of treatment is defined for each subject

as last dose date minus first dose date +1. Duration of treatment will be summarized using the number of subjects treated, mean, standard deviation, median, minimum and maximum. In addition, the number and percentage of subjects in each treatment duration interval (≥ 4 weeks, ≥ 12 weeks, ≥ 24 weeks, ≥ 36 weeks, ≥ 48 weeks) will be summarized for ALL_UPA Population.

Treatment compliance will be summarized by treatment groups for Safety_1 Population and upadacitinib dose groups for ALL_UPA Population. Treatment compliance is defined as the number of tablets actually taken divided by the number of tablets that should have been taken. Percent compliance will be summarized.

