10.2.4 Treatment-Emergent Adverse Events per Patient-Years of Exposure

Exposure-adjusted AEs per 100 patient-years will be provided by SOC and PT, where AEs per 100 patient-years of exposure are defined as the number of AEs divided by the total exposure in 100 patient-years. The study drug exposure is defined as (last dose – first dose) + 1.

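### As written, exposure and Period 2 treatment-emergent events start at the first dose of study drug, which includes placebo, so 12 placebo weeks enter the 15 mg safety summaries

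*SAP*

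**What the plan says.** SAP 10.2.1 defines two treatment-emergent windows. The Period 1 window runs "through 30 days following the last dose of study drug in Period 1 or first dose in Period 2, whichever is" earlier. The other rule reads: "For Period 2, TEAEs are defined as any adverse events that begin or worsen in severity after initiation of study drug through 30 days following"; its end is tied to the final Period 2 dose. The first uses the first Period 2 dose as a boundary; the second does not. No window is defined for the ALL_UPA population.

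SAP 6.0 defines duration of treatment, for each safety population, "as last dose date minus first dose date +1". For event rates, SAP 10.2.4 says "AEs per 100 patient-years of exposure are defined as the number of AEs divided by the total exposure in 100 patient-years", and "The study drug exposure is defined as (last dose – first dose) + 1". Neither formula is limited to upadacitinib or to a period.

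The Operations Manual (Protocol Appendix F), section 6.1, says "Study drug includes the investigational product of upadacitinib and matching upadacitinib placebo". The Safety_1 definition in SAP 4.0 uses the term the same way, because it must take in placebo subjects dosed in Period 1.

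ALL_UPA (SAP 4.0) holds everyone with at least one upadacitinib dose, and so every placebo subject who switches. SAP 10.1 adds: "For ALL_UPA Population, upadacitinib 30 mg, 15 mg and a total group for all subjects on upadacitinib will be summarized".

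**The concern.** A subject randomised to placebo takes the first dose of study drug on Day 1 and the first dose of upadacitinib at Week 12. If the stated rules are programmed as they stand, the 15 mg column of ALL_UPA contains 12 weeks in which no upadacitinib was taken, and the Period 2 window reaches back over Period 1. That second effect is not confined to the switchers: Period 1 events in the 30 mg arm also qualify again as Period 2 events.

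The switchers are the trial's only planned 15 mg data, and their results stand beside those for 30 mg. Rates per 100 patient-years are required for the adverse event overview, serious events, events leading to discontinuation and events of special interest (SAP 10.2.2, 10.2.5, 10.2.6). Two programmers working from this text could produce different tables.

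**Working it through.** **Inputs**
- Placebo 12 weeks and 15 mg 36 weeks (Protocol synopsis).
- Week 12 is Day 85 and Week 48 is Day 336 (Protocol Appendix D).
- Planned N: 40 on upadacitinib, 20 on placebo (SAP 2.2). SAP Appendix F, section 2.1, assumes 45 and 23 for its simulations.
- Assumptions: every placebo subject switches and everyone completes.
- The ratio r = placebo event rate / 15 mg event rate is not in the documents, so a range is shown.

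**1. The plan's own 15 mg duration.** 48 − 12 = 36 weeks. By visit days, 336 − 85 + 1 = 252 days = 36 weeks. The stated duration is reproduced.

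**2. Exposure per completing switcher under the literal rule.** From Day 1 it is 336 days. 336/252 = 1.33, so the denominator is 33% too large.

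**3. Patient-years**

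| Group | From first upadacitinib dose | Literal rule |
|---|---|---|
| 15 mg, N = 20 | 20 × 252/365.25 = 13.8 | 20 × 336/365.25 = 18.4 |
| 15 mg, N = 23 | 23 × 252/365.25 = 15.9 | 23 × 336/365.25 = 21.2 |
| ALL_UPA total, 40 + 20 | (40 × 336 + 20 × 252)/365.25 = 50.6 | 60 × 336/365.25 = 55.2 |
| ALL_UPA total, 45 + 23 | (45 × 336 + 23 × 252)/365.25 = 57.3 | 68 × 336/365.25 = 62.6 |

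The literal ALL_UPA total is about 9% too large in both cases (55.2/50.6 and 62.6/57.3).

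**4. Effect on the 15 mg rate per 100 patient-years.** There are two cases.
- Only events on 15 mg are counted, over 48 weeks: reported/true = 36/48 = 0.75, which is 25% too low.
- Placebo-period events are counted as well: reported/true = (36 + 12r)/48, a 75/25 mix.

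| r (assumed) | 0 | 0.5 | 0.75 | 1 | 1.25 | 1.5 |
|---|---|---|---|---|---|---|
| reported/true | 0.75 | 0.875 | 0.94 | 1.00 | 1.06 | 1.125 |

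**5. Effect on the percentage of subjects with an event.** The literal window contains the true one, so the percentage can only stay equal or rise. As an illustration, take a constant 15 mg rate of 0.5 per patient-year (assumed). Then 1 − exp(−0.5 × 252/365.25) = 29.2%. With the 84 placebo days included, 1 − exp(−0.5 × (252 + 84r)/365.25) gives 33.1% at r = 0.5, 36.9% at r = 1 and 40.4% at r = 1.5.

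**6. Duration categories.** SAP 6.0 reports ALL_UPA subjects with at least 48 weeks of treatment. At 336 days by the literal formula, a switcher with 36 weeks on upadacitinib could be counted there.

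**The case against.** The best defence is that the intent is plain. SAP 10.1 groups subjects by the treatment they actually received and labels the total as subjects on upadacitinib. SAP 6.0 refers to upadacitinib dose groups for ALL_UPA compliance. The Period 1 window closes no later than the first Period 2 dose, and the Period 2 window ends relative to the last Period 2 dose, so the windows look period-specific. A sensible programmer might start the 15 mg clock at the switch without being told.

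Part of this stands. A reader might infer that the SAP deliberately credits placebo time to 15 mg; it does not. No sentence says so, and the result comes from literal wording. But the treatment-received rule assigns subjects to groups, not days or events. A switcher received both placebo and 15 mg, so the rule cannot say when the 15 mg clock starts. The only further rule in SAP 10.1 fixes the actual treatment sequence from Period 1, which for a switcher is placebo. Nothing in the text repairs the start date.

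A reader might also infer that the 15 mg rates are bound to be diluted. The documents do not support that. A certain 25% understatement needs the literal reading for exposure and the sensible reading for events. If both are read literally, the rate may fall, match or rise, depending on a placebo rate that the documents do not give.

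It is also fair to say that the consequence is limited. The trial's objective is 30 mg against placebo, and the 15 mg summaries are descriptive, in about 20 subjects.

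**Conclusion.** The point holds as a defect in the stated rules, not merely as missing detail: followed as written, they give wrong 15 mg and Period 2 figures. The firm figure is 336 rather than 252 days per completing switcher, so that 12 of 48 weeks (25%) of the 15 mg person-time is placebo. The patient-year figures assume full switching and completion. Those at N = 23 also rest on a simulation assumption rather than the planned sample size. The size and sign of the error in the event rate depend on which events are counted, and no fixed direction should be claimed.

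The primary efficacy analysis is unaffected. So is Safety_1 on this point, because Day 1 is the right start for both arms there and the Period 1 event window has its own end. The damage is confined to descriptive ALL_UPA and Period 2 safety summaries, but with roughly 14 to 16 patient-years on 15 mg a 33% error in the denominator is worth removing.

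**What to change.** Amend SAP 6.0, 10.2.1 and 10.2.4 as follows.
- For ALL_UPA, start duration, patient-years and treatment-emergent onset at the first dose of upadacitinib: Day 1 for the 30 mg arm, the first 15 mg dose for switchers.
- For Period 2 summaries, start treatment-emergent onset and exposure at the first Period 2 dose, in both arms.
- End the Period 1 treatment-emergent window before the first Period 2 dose. The present window runs through that dose, so a Period 2 window opening on the same day would count switch-day events in both periods.

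The cost is a few sentences and the matching programming. No new data are needed. The one choice to make is the period for switch-day events. SAP 10.2.1 already treats events on the study drug start date as treatment-emergent, and assigning switch-day events to Period 2 is consistent with that.
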